- For the Safety Evaluation of Combination doses of BMS-986249 with nivolumab (Part 1B), both study treatments will be administered as a co-administration through the same IV bag. Initial dosing will be Q4W co-administration of 240 mg BMS-986249 in combination with 480 mg nivolumab infused over approximately 120 minutes. Infusion times will vary with subsequent co-administration doses to adjust for the different drug protein concentrations. If an alternative dosing schedule is evaluated, co-administration will continue on cycles where both study treatments are scheduled, while nivolumab will be administered IV over approximately 30 minutes when scheduled as a monotherapy.
- In the BMS-986249 in Combination with Nivolumab Randomized Cohort Expansion in Melanoma (Part 2A) cycle length and dose administration will vary with treatment arm.
- In the BMS-986249 in Combination with Nivolumab Additional Tumor Cohort Expansion (Part 2B), participants will receive 1,200 mg BMS-986249 administered IV Q8W in combination with 480 mg nivolumab administered IV Q4W. Co-administration will continue on cycles where both study treatments are scheduled, while nivolumab will be administered IV over approximately 30 minutes when scheduled as a monotherapy.
- Refer to the pharmacy manual for treatment administration, timing, and infusion details for BMS-986249, ipilimumab, and nivolumab.
- BMS-986249 infusions, as a monotherapy or co-administration, will require a 60-minute observation period after the completion of the infusion for the first 3 doses for each participant.
- Tumor progression and response endpoints will be assessed using RECIST v1.1 criteria for solid tumors or PCWG3 (for prostate).

Follow-up:

- Safety Follow-up Period:
 - Upon completion of study therapy (or up to a maximum of 2 years, if applicable) or once the decision is made to discontinue the participant from treatment, that is, at EOT, all participants will enter a Safety Follow-up Period.
 - For participants who complete all scheduled cycles of therapy, the EOT visit will be the same visit as the last scheduled and completed on-treatment visit and will be the start of the Safety Follow-up Period. For participants who do not complete all scheduled cycles of therapy, the EOT visit will be the most recent on-treatment visit (with all available safety and response data) and will not need to be repeated. Accordingly, for these participants, this visit will be considered the start of the Safety Follow-up Period.
 - After the EOT visit, follow-up study visits should occur at Days 30, 60, and 100 (±7 days) for all study participants. Safety reporting of AEs and SAEs should take place from date of informed consent through 100 days post EOT.

 All participants should complete the 3 clinical safety follow-up visits regardless of whether new anti-cancer therapy is started, except those participants who withdraw consent for study participation.

• Imaging Follow-up Period:

At the time of study treatment discontinuation, participants will continue to have radiologic and clinical tumor assessments. The duration of the Imaging Follow-up Period will be 100 days post EOT or until death, or initiation of another anti-cancer treatment, whichever occurs first. Radiological assessments for participants who have ongoing clinical benefit may continue to be collected after participants complete the Survival Follow-up Period of the study. Participants who have disease progression after an initial course of study therapy will be evaluated beyond the EOT visit and will be allowed to receive other tumor-directed therapy as required. The initiation of another anti-cancer treatment will indicate the end of the Imaging Follow-up Period.

• Survival Follow-up Period:

In parallel with the Safety Follow-up Period, all participants will start the Survival Follow-up Period. Since further formal OS analyses will not be conducted, the maximum study duration will be through 100 days post EOT. Participants who are in the follow-up period past 100 days after EOT should be discontinued from the study. Participants will be followed by telephone (from EOT) through 100 days post EOT or until death, loss to follow-up, withdrawal of consent, or conclusion of the study, whichever comes first. For Part 2 participants, EQ-5D-3L data will be collected by telephone or email during the Survival Follow-up Period. Participants will have both the Imaging Follow-up Period and Survival Follow-up Period occur simultaneously. The duration of this follow-up will be through 100 days post EOT. Subsequent therapies will also be recorded in this Survival Follow-up Period.

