To evaluate changes in QoL, health status, ar patient-reported tolerability	Mean scores and post-baseline score changes for all EORTC QLQ-C30 subscales, EQ-5D-3L utility index and VAS, and n (%) of endorsing participants by arm and time point for FACIT GP5 item and PRO-CTCAE items

Abbreviations: ADA = anti-drug antibody; AE = adverse event; DOR = duration of response; EORTC QLQ-C30 = European Organisation for Research and Treatment of Cancer Quality of Life Questionnaire – Core 30; EQ-5D-3L = European Quality of Life – 5 Dimension – 3 Level Questionnaire; FACIT GP5 = Functional Assessment of Chronic Illness Therapy General Physical item 5; ORR = objective response rate; OS = overall survival; PFS = progression-free survival; PK = pharmacokinetics; PRO-CTCAE = Patient-reported Outcomes version of the Common Terminology Criteria for Adverse Events; QoL - Quality of Life; RECIST = Response Evaluation Criteria in Solid Tumors; SAE = serious adverse event; TTR = time to response; VAS = visual analogue scale.

Table 1-3: Objectives and Endpoints: The Dose Expansion Phase in Additional Tumors (Part 2B)

	Objectives	Endpoints				
Pr	imary					
•	To evaluate the preliminary safety and tolerability of BMS-986249 in combination with nivolumab in participants with previously treated HCC, CRPC, and TNBC.	Incidence of treatment-related Grade 3-5 AEs within 24 weeks				
Se	condary					
•	To assess the preliminary anti-tumor activity of BMS-986249 in combination with nivolumab in participants with previously treated HCC, CRPC, and TNBC	ORR, DOR, PFS, and TTR as assessed by investigator per RECIST v1.1 or PCWG3 (for prostate cancer). PSA response rate for prostate cancer				
•	To characterize the safety and tolerability of BMS-986249 in combination with nivolumab in participants with previously treated HCC, CRPC, and TNBC	Incidence of AEs, SAEs, AEs leading to discontinuation, death, and laboratory abnormalities				
•	To characterize the PK of BMS-986249 when administered in combination with nivolumab in participants with previously treated HCC, CRPC, and TNBC	Summary measures of PK parameters of BMS-986249 in combination with nivolumab				
Ex	ploratory					
•	To explore the associations between PK of	Association measures between BMS-986249				
	BMS-986249 and nivolumab, safety, efficacy, and clinical biomarkers such as, but not limited to T-cell specific genes	and nivolumab PK levels, select outcomes, and biomarkers of interest				

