2 SCHEDULE OF ACTIVITIES

Study assessments and procedures are shown in Table 2-1, Table 2-2, Table 2-3, Table 2-4, and Table 2-5.

In limited instances, scheduled events (including events other than safety assessments) can occur outside of the indicated timeframes but the Sponsor should first be notified.

If a participant has a delay in study treatment administration for any reason, then assessments and laboratory tests (with the exception of any tests needed to ensure participant safety) should be correspondingly delayed with the exception of tumor assessments. Tumor assessments continue per protocol schedule regardless of any treatment delay incurred.

The pharmacokinetic (PK), and safety profiles of BMS-986249 are being elucidated, modifications to the procedures (ie, reduction in PK, sampling, timing of procedures, dose schedules) currently outlined in Section 2 and Section 9 may be required. These modifications will not include the addition of new procedures and will be documented in a note to file or administrative letter.

In the event that multiple procedures are required at a single time point, the electrocardiogram (ECG) may be obtained up to 15 minutes earlier, vital signs may be obtained up to 10 minutes earlier or later, and clinical laboratory samples may be obtained up to 5 minutes earlier than the nominal time point, ensuring the PK samples can be collected on time.

 Table 2-1:
 Screening Schedule of Activities for All Study Parts

Procedure	Screening Visit (Days -30 to -1)	Notes					
Eligibility Assessments							
Informed Consent	X	Must be obtained prior to performing any screening procedures. A participant is considered enrolled only when a protocol-specific ICF is signed.					
Contact IRT	X	After the participants meet all eligibility criteria, sites will use IRT for participant number assignment. Register in IRT to obtain participant number. Subsequent visits will be registered into the IRT system for drug supply. See Section 5.1.1. If the IRT system is not available, participants will be enrolled manually. The participant number will be created in the IRT system upon availability.					
Inclusion/Exclusion Criteria	X	Must be confirmed prior to randomization/treatment assignment. See Section 6.1 and Section 6.2.					
Medical History	X	All medical history relevant to the disease under study. Include any toxicities or allergies related to previous treatments.					
Prior Cancer Therapies	X						

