On-treatment Tumor Biopsy	For Part 2A: The on-treatment biopsy will be collected on participants treated (about 25 participants per active Arm), and then collected per Investigator preference on per active Arm) for approximately the next 105 participants treated (about 35 participants per active Arm)										
Required Post- progression Tumor Biopsy				See Section 9.8.2							
Exploratory Biomarker Assessments											See Sections 9.5, 9.8, and Table 9.8.3-1 for all required collections.
Clinical Treatment S	upplies										
Randomization	day o		nt on Cyc						orior to the first the Medical		For Part 2A, PD-L1 result required for randomization.

Protocol Amendment No.: 09 Date: 14-Mar-2023

Approved v1000 930119402 10.0

Table 2-4: On-treatment Schedule of Activities for Part 2A Arm B and Arm C, and Part 2B

		Cy	vcle 1			Сус	ele 2		Cycles 3 and Beyond		
Procedure		(28 days	s in lengt	ch)	(28 days i	in length)		(each cycle 28 days in length)	EOT ^{a,b}	Notes
	D1	D8	D15	D22	D1	D8	D15	D22	D1		
		(± 2 days)	(± 2 days)								
									X		
BMS-986249 Administration Q8W (Part 2A Arm B and Arm C, and Part 2B)	X								Every other cycle starting at C3 [eg, C3, C5, C7, etc]		BMS-986249 to be supplied by BMS.
Nivolumab Administration Q4W (Part 2A Arm B and Arm C, and Part 2B)	X				X				X		Nivolumab to be supplied by BMS.
Patient-Reported Out	comes										See Section 9.9
EORTC QLQ-C30	X				X				X	X	For C1D1, performed after randomization but prior to first dose. All other cycles collected prior to dosing.
EQ-5D-3L	X				X				X	X	For C1D1, performed after randomization but prior to first dose. All other cycles collected prior to dosing.
FACIT GP5	X	X	X	X	X	X	X	X	X	X	For C1D1, performed after randomization but prior to first dose. All other cycles collected prior to dosing.

Table 2-4: On-treatment Schedule of Activities for Part 2A Arm B and Arm C, and Part 2B

	Cycle 1				Cycle 2				Cycles 3 and Beyond		Notes
Procedure	(28 days in length)				(28 days in length)			(each cycle 28 days in length)	EOT ^{a,b}		
D1	D1	D8	D15	D22	D1	D8	D15	D22	D1		
		(± 2 days)	(± 2 days)	(± 2 days)	(± 2 days)	(± 2 days)	(± 2 days)	(± 2 days)	(± 2 days)		
PRO-CTCAE	X	X	X	X	X	X	X	X	X	X	For C1D1, performed after randomization but prior to first dose. All other cycles collected prior to dosing.

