5.1.5 Follow-up

5.1.5.1 Safety Follow-up Period

Upon completion of study therapy (or up to a maximum of 2 years, if applicable) or once the decision is made to discontinue the participant from treatment, that is, at end of treatment (EOT), all participants will enter a Safety Follow-up Period.

For participants who will complete all scheduled cycles of therapy, the EOT visit will be the same visit as the last scheduled and completed on-treatment visit and will be the start of the Safety Follow-up Period. For participants who will not complete all scheduled cycles of therapy, the EOT visit will be the most recent on-treatment visit (with all available safety and response data) and will not need to be repeated. Accordingly, for these participants, this visit will be considered the start of the Safety Follow-up Period.

After the EOT visit, follow-up study visits should occur at Days 30, 60, and 100 (±7 days) for all study participants. Safety reporting of AEs and SAEs should take place from date of informed consent through 100 days post EOT.

All participants should complete the 3 clinical safety follow-up visits regardless of whether new anti-cancer therapy is started, except those participants who withdraw consent for study participation.

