 - Dosing delays lasting > 8 weeks from the previous dose that occur for non-drug-related reasons may be allowed if approved by the Medical Monitor (or designee).
- For Part 2A Arms A and D during the Combination Therapy Phase, decisions to discontinue study treatment therapy must include both nivolumab as well as BMS-986249 or ipilimumab. It is not permitted to continue nivolumab without BMS-986249 or ipilimumab. Part 2A Arm A and D participants who do not complete all scheduled cycles of BMS-986249 or ipilimumab and nivolumab combination therapy will not be eligible for the nivolumab monotherapy Maintenance Phase.
- For Part 1B, Part 2A Arms B, C, and F, and Part 2B, the assessment for discontinuation of nivolumab should be made separately from the assessment made for discontinuation of BMS-986249, if possible. Although there is overlap among the discontinuation criteria, if discontinuation criteria are met only for BMS-986249 but not for nivolumab, treatment with nivolumab may continue after discussion and approval by the Medical Monitor (or designee). Treatment with BMS-986249 may continue if nivolumab is discontinued only if the investigator is able to clearly determine the discontinuation event is only related to nivolumab treatment and the decision is discussed with and approved by the Medical Monitor (or designee).

BMS-986249, as a Probody of ipilimumab, is predicted to have a similar but attenuated irAE profile compared to ipilimumab. The activation of a pre-existing but attenuated immune response

to cancer by checkpoint blockade is associated with an AE profile that is inherent to immune activation. Hence, distinguishing between an ipilimumab and nivolumab AE can be difficult. Clinical trial experience and labeled indications have characterized the AE profiles of ipilimumab and nivolumab and suggest that some events are more frequently associated with a specific agent (eg, pneumonitis is more common with nivolumab than ipilimumab). Listed below are the most common irAE and AEs of ipilimumab and nivolumab. Refer to section 7.5.1 for information on DLTs.

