10.3.2 Safety Analyses

All safety analyses will be performed on the treated population. See Table 10.3.2-1 for a description of the safety analyses.

Table 10.3.2-1: Safety - Statistical Analyses

Endpoint	Statistical Analysis Methods
Incidence of DLTs (Part 1 only), AEs, SAEs, AEs leading to discontinuation, and death AEs will be graded according to CTCAE v4.03	DLT rate by dose level, frequency distribution of treated participants with AE using the worst CTC grade. Participants will be counted only (1) once at the PT level, (2) once at the system organ class level, and (3) once in the "total participant" row at their worst CTC grade, regardless of system organ class or PT.
Incidence of treatment-related Grade 3-5 AEs within 24 weeks	Incidence rate (Part 2A, Part 2B) along with the ratio and difference in incidence rates (Part 2A) will be presented by point estimates and CIs ^a (Parts 2A and 2B)
Laboratory abnormalities Laboratory values will be graded according to CTCAE v4.03.	Laboratory shift table using the worst CTC grade on treatment per participant

Abbreviations: AE = adverse event; CTC = common terminology criteria; CTCAE = Common Terminology Criteria for Adverse Events; DLT = dose-limiting toxicity; PT = preferred term; SAE = serious adverse event.

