10.3.7 Patient-Reported Outcome Analyses

PRO analyses are described in Table 10.3.7-1.

Table 10.3.7-1: PRO - Statistical Analyses

[figure not shown]
Secondary Endpoint	Statistical Analysis Methods
To evaluate TTD in Global Health Status/QoL of the EORTC QLQ-C30 (Part 2A only)	TTD in Global Health Status/QoL and Physical Functioning will be defined as the time from randomization until a clinically meaningful decline (ie, reduction ≥10 points) from baseline in EORTC QLQ-C30 global health/quality of life subscale score and Physical Functioning Scale score. Estimates for both Global Health Status/QoL and Physical Functioning will be provided with associated 95% CIs.
To evaluate TTD in Physical Functioning Scale of the EORTC QLQ-C30 (Part 2A only)	The analysis will use all available data from randomized participants, including data collected during post-treatment follow up. Median deterioration times, hazard ratios, and 95% CIs will be calculated

Abbreviations: CI = confidence interval; EORTC = European Organisation for Research and Treatment of Cancer; PRO = patient-reported outcome; QLQ-C30 = Quality of Life Questionnaire – Core 30; QoL = quality of life; TTD = time to deterioration.

Analyses of PRO will be performed on participants who have an assessment at baseline and at least 1 post-baseline assessment.

Further exploratory analyses for Part 2A and Part 2B not specified here will be described in the Statistical Analysis Plan, which will be finalized before database lock and may be presented separately from the main clinical study report.

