Authorship of publications at BMS is aligned with the criteria of the International Committee of Medical Journal Editors (ICMJE, www.icmje.org). Authorship selection is based upon significant contributions to the study (ie, ICMJE criterion #1). Authors must meet all 4 ICMJE criteria for authorship:

- 1) Substantial intellectual contribution to the conception or design of the work; or the acquisition of data (ie, evaluable subjects with quality data), analysis, or interpretation of data for the work (eg, problem solving, advice, evaluation, insights and conclusion); AND
- 2) Drafting the work or revising it critically for important intellectual content; AND
- 3) Final approval of the version to be published; AND

4) Agreement to be accountable for all aspects of the work in ensuring that questions related to the accuracy or integrity of any part of the work are appropriately investigated and resolved.

Those who make the most significant contributions, as defined above, will be considered by BMS for authorship of the primary publication. Sub-investigators will generally not be considered for authorship in the primary publication. Geographic representation will also be considered.

Authors will be listed by order of significant contributions (highest to lowest), with the exception of the last author. Authors in first and last position have provided the most significant contributions to the work.

For secondary analyses and related publications, author list and author order may vary from primary to reflect additional contributions.

APPENDIX 3

ADVERSE EVENTS AND SERIOUS ADVERSE EVENTS: DEFINITIONS AND PROCEDURES FOR RECORDING, EVALUATING, FOLLOW UP AND REPORTING

ADVERSE EVENTS

Adverse Event Definition:

An Adverse Event (AE) is defined as any new untoward medical occurrence or worsening of a preexisting medical condition in a clinical investigation participant administered study treatment and that does not necessarily have a causal relationship with this treatment.

An AE can therefore be any unfavorable and unintended sign (such as an abnormal laboratory finding), symptom, or disease temporally associated with the use of study treatment, whether or not considered related to the study treatment.

Events Meeting the AE Definition

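### The stated PRO-CTCAE summary gives prevalence by visit, not how many participants newly developed or worsened a symptom; a baseline-referenced count would be a cheap addition

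*Combined protocol and SAP*

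**What the plan says.** The endpoint tables (Synopsis, Tables 1-2 and 1-3; Section 4, Tables 4-2 and 4-3) carry an exploratory objective of evaluating change in quality of life, health status and patient-reported tolerability. For QLQ-C30 and EQ-5D-3L the endpoint includes change from baseline. For the other two instruments it is "n (%) of endorsing participants by arm and time point for FACIT GP5 item and PRO-CTCAE items".

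Section 10.3.7 specifies an analysis only for QLQ-C30 time to deterioration, then adds: "Further exploratory analyses for Part 2A and Part 2B not specified here will be described in the Statistical Analysis Plan". The file supplied contains no separate SAP text.

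The baseline needed for a within-participant comparison exists. Tables 2-2, 2-3 and 2-4 schedule PRO-CTCAE at C1D1: "For C1D1, performed after randomization but prior to first dose". The PRO population in Table 10.2-1 already requires a baseline and at least one later assessment.

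The protocol's clinician-reported side already handles both onset and severity. Appendix 3 defines an adverse event as "any new untoward medical occurrence or worsening of a preexisting medical condition in a clinical investigation participant", and Table 10.3.2-1 plans a "frequency distribution of treated participants with AE using the worst CTC grade", counting each participant once.

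**The concern.** Counts by visit are marginal totals. They show whether more or fewer participants report a symptom than at C1D1, but not who changed. Resolution in some participants can cancel onset in others, so a flat prevalence can hide many new cases.

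The protocol does not say what *endorsing* means. If it means any score above none, a participant who moves from mild to severe counts the same at both visits, although Section 5.4.10 says the items assess severity, frequency and interference.

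Section 9.9.4 includes these items because clinicians under-report symptomatic toxicity. As stated, the summary does not give the patient-reported counterpart of the adverse event tables: how many participants had a symptom that was new or worse after treatment began.

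**Working it through.** The plan attaches no sample size, power or other figure to this endpoint, so there is none to reproduce.

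**1. What marginal counts leave open.** Let n participants have forms at C1D1 and at one later visit, with b endorsing at C1D1 and v later. The number newly endorsing lies between max(0, v − b) and min(v, n − b). If *endorsing* means any score above none, the number new or worse lies between max(0, v − b) and v. The counts below are assumed; n is the planned size of a Part 2A arm (60) or a Part 2B cohort (40).

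| n | b | v | Newly endorsing | New or worse |
|---|---|---|---|---|
| 60 | 18 | 18 | 0 to 18 | 0 to 18 |
| 60 | 18 | 24 | 6 to 24 | 6 to 24 |
| 60 | 30 | 30 | 0 to 30 | 0 to 30 |
| 40 | 16 | 20 | 4 to 20 | 4 to 20 |
| 40 | 24 | 28 | 4 to 16 | 4 to 28 |

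**2. Forms scheduled after C1D1, with no dose delays.**

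- Arms C and F (Tables 2-4 and 2-2): weekly in two 28-day cycles, then Day 1 of each cycle. This gives Days 8, 15, 22, 29, 36, 43, 50, 57, 85, 113 and 141, which is 11 forms through Day 168.
- Arm D (Table 2-3, then Table 2-2 from Cycle 5): weekly in four 21-day cycles, then Day 1 of each 28-day cycle from Day 85. This gives the same 11 days plus Days 64, 71 and 78, which is 14 forms.
- Day 169 is a scheduled visit in all three arms and falls exactly 24 weeks after a Day 1 first dose. If the window includes it, the counts are 12 and 15, and the difference is still three.

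**3. Effect of the number of forms.** Assume each form independently has chance q of scoring above C1D1. The chance that the worst of m forms exceeds C1D1 is 1 − (1 − q)^m.

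| q | m = 11 | m = 14 | Gap (points) |
|---|---|---|---|
| 0.01 | 10.5% | 13.1% | 2.7 |
| 0.05 | 43.1% | 51.2% | 8.1 |
| 0.10 | 68.6% | 77.1% | 8.5 |

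The gap, computed before rounding, is an artefact against Arm D with no true difference. It is smaller if scores are correlated within participants. Using only the common days removes this scheduling difference.

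The m = 11 column matters in its own right. If rises above C1D1 were only ordinary fluctuation, about 10% to 69% of participants would be flagged with no drug effect, or fewer with correlated scores.

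**4. Precision in Part 2A.** With 60 per arm and a common rate p, the 95% half-width for a difference is 1.96 × √(2p(1 − p)/60): 10.7 points at p = 0.1, 16.4 at 0.3 and 17.9 at 0.5. The comparison can only be descriptive.

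**The case against.** The strongest objection is that nothing here is wrong. The quoted wording sits in an endpoint table, the endpoint is exploratory, and Section 10.3.7 sends further analyses to the SAP. A reader might infer that no within-participant PRO-CTCAE analysis is planned. The documents do not support that. They show only that none is stated.

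A second objection is that the added statistic is noisy. A maximum over about 11 forms against one baseline form rises with ordinary fluctuation, and a participant whose disease progresses also counts as worse. A reader might think the addition most valuable in Part 2B, where there is no comparator. The opposite holds: in Part 2A the concurrent Arm D gives a reference for this background, and in Part 2B nothing does. This objection stands and limits how the Part 2B figure may be read.

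Third, the ranges in the first table are logical extremes for a single visit under assumed counts. They show what the by-visit table cannot determine, not what the 24-week statistic would gain. If the SAP tabulates each response level, shifts in severity would show in the by-visit distribution, though still not within participants. Both points stand.

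None of this restores the missing information: counts by visit cannot give the number of participants who became new or worse cases.

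**Conclusion.** The point holds as an optional improvement to one exploratory summary. The only stated PRO-CTCAE summary shows net change in prevalence from C1D1. It leaves the number of new or worsened cases undetermined, by as much as 0 to 18 of 60 when 18 endorse at both visits. That example rests on assumed counts and complete forms; the underlying limitation does not depend on them. The 3 to 9 point scheduling artefact rests on independent forms with q between 1% and 10%.

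A reader might also infer that differential drop-out biases the by-visit table in favour of one arm. The documents support neither a size nor a direction. Under Section 8.1, in Arms C and F "treatment with nivolumab may continue after discussion and approval by the Medical Monitor", yet both drugs stop when attribution is unclear, and Arm D participants who do not complete the combination cannot enter maintenance. No claim about attrition bias is made.

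**What to change.** In the SAP, labelled exploratory:

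- Keep the by-visit table, and define *endorsing* and the denominator.
- For each PRO-CTCAE item, add the number and percentage of the PRO population whose worst post-baseline score within 24 weeks of first dose exceeds their C1D1 score.
- For Part 2A, describe C versus D and F versus D on nominal days common to all arms: weekly from Day 8 to Day 57, then Days 85, 113 and 141, plus Day 169 if the window is defined to include it. Assign forms by visit window, since after a dose delay assessments "should be correspondingly delayed with the exception of tumor assessments".
- Report the number of forms completed by arm. State whether safety follow-up forms within 24 weeks count, since participants are asked to "complete the 3 clinical safety follow-up visits regardless of whether new anti-cancer therapy is started, except those participants who withdraw consent".
- For Part 2B, present the figure only as a description of new or worse symptoms, not as a drug effect.

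The cost is SAP wording, one derived variable per item, the visit windows and a table of form counts. All forms are already scheduled. The downside is that a maximum hides timing, which the by-visit table still shows, and depends on how many forms each participant completes, which is why that number should be reported beside it.
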